### 13. SPECIMEN BANKING

- *If specimens will be banked for future research, describe where the specimens will be stored, how long they will be stored, how they will be accessed and who will have access to the specimens*
- *List the information that will be stored with each specimen, including how specimens are labeled/coded*
- *Describe the procedures to release the specimens, including: the process to request release, approvals required for release, who can obtain the specimens, and the information to be provided with the specimens.*

N/A

### 14. DATA MANAGEMENT AND CONFIDENTIALITY

- *Describe the data and specimens to be sent out or received. As applicable, describe:*
  - *What information will be included in that data or associated with the specimens?*
  - *Where and how data and specimens will be stored?*
  - *How long the data will be stored?*
  - *Who will have access to the data?*
  - *Who is responsible for receipt or transmission of data and specimens?*
- *Describe the steps that will be taken to secure the data during storage, use and transmission.*

Data management in this study varies according to phase of study participation. Individuals who are participating in preliminary study phases will engage with the study team through secure Northwell emails via Northwell's Office 365 Microsoft Teams application or by phone. Email communication and documentation of feedback shared during Teams meetings will be retained in a Sharepoint folder on the Northwell network, accessible only to IRB approved study personnel.

Electronic informed consent and demographic information will be retained in the study database (N1Thrive/REDCap).

#### Fitbit

This pilot study uses Fitbit devices to remotely monitor participant activity and sleep. All enrolled participants will be provided with a study account that has been created by the research team with no identifying information to the participant. The email address of the study account contains a unique identifier (e.g. northwellf25). Data collected by the activity monitor may include daily steps, floors climbed, activity intensity, heart rate, sleep duration, and estimated minutes in sleep stages. A file linking the Fitbit identifier to the study participant will be housed in a Northwell-approved drive to store PHI, and be accessible only by members of the study team listed in the IRB application. Coded data from Fitbit will remain stored in a Northwell-approved drive indefinitely, but the file linking the Fitbit identifier to the study participant will be destroyed upon completion of an individual's participation with the study.

#### Fitabase

The Personalized Trial Study will use Fitabase to retrieve Fitbit data from participant activity tracking devices. Fitabase is a secure, online portal. The Fitbit study account provided to the participants will be linked to an identification number in the Fitabase system (e.g. FLT01). No information that could be used to identify a participant will be stored on Fitabase. Only the research team will have access to data that will be able to connect a research participant to their Fitabase ID. Data collected may include last sync date, battery charge status, daily steps, floors climbed, activity intensity, heart rate, sleep duration, and estimated minutes in sleep stages. Fitabase will stop tracking participant data at the trial end date selected by the research coordinator. As an added measure, participants will be instructed to remove the Fitbit study account from their device if they plan to keep the Fitbit.

#### Personalized Trial Consent, Fitbit data, Study Messages and Surveys

This study will utilize a technology platform to support the delivery of Personalized Trials. To achieve this goal, we are partnering with a company called N-1 Thrive, a Northwell approved system for collecting and storing research data, including PHI that was formed specifically for the development of technology to support Personalized Trial methodology. Informed consent, study messages and surveys (BCT & satisfaction surveys) will be delivered via a text-message link to a secure, HIPAA compliant web browser through N-1 Thrive/REDCap. In addition, the Personalized Trial portion of the study will use N1Thrive to retrieve Fitbit data from participant activity tracking devices. Coded data using unique generic participant IDs will be shared with 4Peacocks in order to assist with analyzing the individual reports and to pool of N-of-1 results across all projects using the N1Thrive platform. This analysis will be done by unique identifier. Coded reports will be given back to the study team, who will identify the document before

sending to the participant via encrypted email. Pooled N-of-1 results will be used to assess gaps in phenotypic understanding to empirically determine if modeling precise therapy is feasible.

The study team takes data confidentiality very seriously. The participant will be made aware of all data collected and the companies/technology employed to collect the data via the consent process. All data will be maintained on a Northwell-approved drive to store PHI. Data collected for this study will be maintained in its original and unaltered source data state in a Northwell-approved SQL database on a Northwell-approved drive to store PHI indefinitely. Data collected under this research may be used for future research in coded format without additional consent as per the consent form participants sign and with appropriate IRB approval as required. Any additional data that must be shared will be done so according to the consent form participants signed. Only research staff listed within this IRB submission will have access to identifiable information. Anonymized data may be stored indefinitely for reference following the conclusion of the study. All members of the research team with access to directly identifiable data will be trained and included on the IRB submission for approval. Regular meetings will take place with the PI and other members of the study team to ensure protocol adherence and data accuracy.

## 15. DATA AND SAFETY MONITORING PLAN

*A specific data and safety monitoring plan is only required for greater than minimal risk research. For guidance on creating this plan, please see the [Guidance Document](#) on the HRPP website.*

*Part I – this part should be completed for all studies that require a DSMP.  
Part II – This part should be completed when your study needs a Data and Safety Monitoring Board or Committee (DSMB/C) as part of your Data and Safety Monitoring Plan.*

### Part I: Elements of the Data and Safety Monitoring Plan

- *Indicate who will perform the data and safety monitoring for this study.*
- *Justify your choice of monitor, in terms of assessed risk to the research subject's health and well being. In studies where the monitor is independent of the study staff, indicate the individual's credentials, relationship to the PI, and rationale for selection*
- *List the specific items that will be monitored for safety (e.g. adverse events, protocol compliance, etc)*
- *Indicate the frequency at which accumulated safety and data information (items listed in # above) will be reviewed by the monitor (s) or the DSMB/C.*
- *Where applicable, describe rules which will guide interruption or alteration of the study design.*
- *Where applicable, indicate dose selection procedures that will be used to minimize toxicity.*

- *Should a temporary or permanent suspension of your study occur, in addition to the IRB, indicate to whom will you report the occurrence.*

Given that study activities involve no more than risks encountered in daily life (increased time spent walking by healthy, working individuals), the study has received approval from the NIA for a safety monitor. [name] has been approved to provide safety monitoring for this pilot. [name] is a family medicine clinician and oversees Northwell's Health Solutions programs.

Although it is not anticipated that increased low-intensity walking by healthy employees poses greater risk than daily life, participants will be advised to report any potential adverse events such as increased fatigue or muscle soreness related to increased walking. [name] will be immediately informed of any serious adverse events along with the study PI. Events will be reported to the IRB according to local policy and NIA as indicated. Additionally, [name] will review participation and attrition from the personalized trial on a monthly basis.

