receive up to four text message prompts per day. They will complete a measure of self-efficacy (i.e. confidence in their ability to walk without stopping) and a ‘satisfaction with BCT’ survey once every two weeks. At the end of their trial, participants will receive a satisfaction survey and a summary of their observed data to help them learn more about their responses to the four behavioral change techniques and to inform investigators as to the feasibility of N-of-1 study design for future research and clinical applications.

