#### Intervention Delivery

This pilot study will use text messages to deliver four behavioral change techniques identified in Michie et al.’s (2011) paper which identified those BCTs associated with influencing change in physical activity behavior. These BCTs were updated to align with current BCT definitions using Michie et al.’s (2013) Taxonomy of Behavioral Change Techniques. A list of BCTs is provided as an appendix to this protocol. Participants will also receive **bi-weekly surveys** to assess their satisfaction with the given BCT and walking self-efficacy. BCTs will be provided to participants in a randomized crossover design with each BCT delivered individually in one of four 2-week blocks. The order in which participants receive BCTs will be randomized with the randomization order determined by the study

statistician. Prior to BCT delivery (i.e. every two weeks) participants will be sent information/BCT descriptions the day before they start their new BCT so that they understand the differences between the four BCTs for their personalized trial. For instance, BCT descriptions may include:

BCT Name	Definition	Sample Text Message Prompt
Goal Setting Behavior	Set or agree on a goal defined in terms of behavior to be achieved	Set the goal of being more active today. Record your goal
Action Planning	Prompt detailed planning of performance of behavior (must include a setting frequency, duration, and intensity)	“It’s Tuesday. Walk 2,000 steps from 10am -11am this morning.”
Self-Monitoring of Behavior	Establish a method for person to monitor and record their number of active periods based on their Fitbit	“It’s time to check your FitBit dashboard and view how active you have been today.”
Feedback on Behavior	Monitor and provide informative or evaluative feedback on performance of the behavior (e.g. form, frequency, duration, intensity)	“You met your goal yesterday. You walked 2,000 steps more than baseline.”

Participants may receive additional text messages to those outlined above with important reminders to sync their data as needed.

Upon completion, participants in the personalized trials phase will receive an individual report that demonstrates their walking responses in relation to their assigned BCTs and a satisfaction survey to obtain feedback about their personalized trials experience.

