## 17. RISKS TO SUBJECTS

- *Describe any potential risks and discomforts to the subject (physical, psychological, social, legal, or other) and assess their likelihood and seriousness and whether side effects are reversible. Where appropriate, describe alternative treatments and procedures that might be advantageous to the subjects.*
- *Include risks to others, like sexual partners (if appropriate)*
- *Discuss why the risks to subjects are reasonable in relation to the anticipated benefits and in relation to the importance of the knowledge that may reasonably be expected to result*
- *Describe the procedures for protecting against or minimizing any potential risks, including risks to confidentiality, and assess their likely effectiveness.*

The study poses low risk of physical harm to subjects as participants are community dwelling employees, report themselves as healthy, walk regularly and have never been advised by a clinician that increasing low intensity walking would be unadvisable/present a safety issue. It is possible that participants may experience muscle soreness or fatigue related to increasing their walking. Completion of validated questionnaires and text message delivery of BCTs has not been shown to increase risk to study participants.

The primary risk to participants is the potential risk of loss of privacy of information pertaining to research material collected by the study, we will take precautions, described below, to minimize these risks.

We will emphasize to subjects involved in all study phases that they can stop and withdraw from the preliminary phases and/or the N-of-1 trial completely at any point.

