The study team plans to protect privacy by only sharing necessary information about participants with those who receive IRB approval to join the study team. All participants will be informed that their responses are confidential and that they may refuse to participate in the project or withdraw at any time without explanation, and that such action will not affect their future interactions with their employment, ability to receive health care or to participate in other research studies. The risk of loss of confidentiality will be minimized by securely storing data including PHI in a Northwell-approved platform and minimizing the use of PHI. To ensure confidentiality, all data containing personal identifiers, and used to track contact with participants will be kept in a secure, password-protected, encrypted Northwell-approved platform (REDCap, Sharepoint and/or N1Thrive). No paper documents with personal identifiers will be kept. The PI will be responsible for ensuring that the confidentiality of the data is maintained at all times. All data will be obtained specifically for research purposes.

Personal or identifiable information is not stored on any of the study devices used in this study. No information about the participants or the participants' health history will be shared with Fitbit, except for the information the participants directly share themselves should they choose to use the device for personal use at the conclusion of the study. There is no additional risk with using Fitbit as part of this research study as compared to using the device as a consumer, including mild skin irritation (i.e. contact dermatitis) which occurs among a small proportion of users. Participants will be instructed via the consent form on methods to reduce irritation (i.e. keep the band clean and dry) and that they can remove the band for a short period of time.

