## **18. RESEARCH RELATED HARM/INJURY**

- *Describe the availability of medical or psychological resources that subjects might need as a result of anticipated problems that may be known to be associated with the research.*
- *If the research is greater than minimal risk, explain any medical treatments that are available if research-related injury occurs, who will provide it, what will be provided, and who will pay for it.*

Should a participant experience an adverse event, they will be advised to notify a study coordinator and contact their primary care provider. The study will immediately notify the safety monitor, [name], the PI, and the IRB according to timelines established in the study's manual of operations. Should a participant report emotional distress in responding to survey questions, the research coordinators will refer to a licensed clinical psychologist in our center, who will recommend follow-up.

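### Adverse events are collected only by spontaneous report, so a low count could not be read as a low event rate; one question in the existing two-weekly surveys would be a cheap improvement

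*Combined protocol and SAP*

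**What the plan says.** Two sections describe how adverse events reach the study team.

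- **Section 15, Part I:** "participants will be advised to report any potential adverse events such as increased fatigue or muscle soreness related to increased walking".
- **Section 18:** "Should a participant experience an adverse event, they will be advised to notify a study coordinator and contact their primary care provider".

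The protocol names the physical effects it expects. Section 17 says "It is possible that participants may experience muscle soreness or fatigue related to increasing their walking", and for the Fitbit it adds ordinary consumer risk, "including mild skin irritation (i.e. contact dermatitis) which occurs among a small proportion of users".

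Regular contact with participants already exists. Section 2 describes a "survey once every two weeks", and Section 11 (Intervention Delivery) gives the purpose of the surveys: "to assess their satisfaction with the given BCT and walking self-efficacy". During the two-week baseline, participants acknowledge a daily text. Those below 80% on Fitbit wear and text response are not randomized (Section 11).

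For oversight, the safety monitor hears at once of serious events and looks at participation and attrition each month (Section 15, Part I). No scheduled review of non-serious events is described. Section 10 lists no safety endpoint, and Section 12 describes no analysis of adverse events.

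**The concern.** There are no visits at which soreness, fatigue or a skin reaction would be noticed in passing. As described, an event is recorded only if the participant decides to raise it.

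Two features of the plan make silence more likely. Section 16 lists side effects that participants themselves report among the reasons for removing someone without their consent. Section 6 ties the $100 pay card to completing all study requirements. A participant with mild soreness could reasonably fear losing both the trial and the payment by mentioning it.

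At stake is what can be said about tolerability afterwards. The pilot is meant to inform wider use of this design. A handful of volunteered events could mean few events or few reports, and the plan has no means of telling these apart. Without a question at baseline there is also no background rate of soreness or fatigue to set beside the intervention period.

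**Working it through.** **Step 1: what is described.** The table sets the contacts and rules in the protocol side by side.

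| Contact or rule | Section | Described content | Asks about events? |
|---|---|---|---|
| Instruction to report | 15, Part I | Participant comes forward | No |
| Adverse event procedure | 18 | Participant notifies coordinator | No |
| Two-weekly survey | 2, 11 | Technique satisfaction, walking self-efficacy | Not described |
| Daily baseline text | 11 | Acknowledgement of receipt | Not described |
| End-of-trial survey | 2, 11 | Satisfaction | Not described |
| Monthly monitor review | 15, Part I | Participation and attrition | Not described |

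**Step 2: size, as an illustration.** The documents give no adverse event rate, reporting rate or safety threshold, and the sample size rests on feasibility (Section 12). There is therefore no figure of the plan's own to reproduce.

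Inputs:
- *n* = 60, the maximum number randomized (Section 8).
- *s*, the fraction of affected participants who report: assumed, with a range shown.
- *p*, the true proportion of participants affected: assumed where used.
- Participants are treated as independent, each counted once.

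If nobody reports an event, the upper one-sided 95% limit on the reported proportion is 1 − 0.05^(1/60) = 0.0487, or 4.9%. The limit on the true proportion is this divided by *s*:

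- *s* = 1: 4.9%
- *s* = 0.50: 0.0487 / 0.50 = 9.7%
- *s* = 0.30: 0.0487 / 0.30 = 16.2%
- *s* = 0.20: 0.0487 / 0.20 = 24.4%

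**Step 3: the same point from the other side.** Suppose the true proportion is 10%. Then P(no reports) = (1 − 0.10*s*)^60, and P(at most one report) adds 60 × 0.10*s* × (1 − 0.10*s*)^59.

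| *s* | P(no reports) | P(at most one report) |
|---|---|---|
| 1 | 0.2% | 1.4% |
| 0.50 | 4.6% | 19.2% |
| 0.25 | 21.9% | 55.6% |
| 0.10 | 54.7% | 87.9% |

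With complete capture, seeing at most one report would be strong evidence against a 10% rate. With a quarter of events reported, it is more likely than not. Since *s* is unknown, and the plan offers no way to estimate it, the count alone cannot separate the two.

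**The case against.** Several points on the other side stand and limit what can be claimed.

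- **The risk statement.** A reader might infer that the plan relies on event counts to prove low risk, so that weak capture undermines its own claim. The text does not support this. "Given that study activities involve no more than risks encountered in daily life (increased time spent walking by healthy, working individuals" is a premise stated in advance to justify a safety monitor and no DSMB. Section 17 rests the low physical risk on the population: healthy regular walkers never advised against more walking. Nothing says that counts will test it.
- **Unseen instruments.** A reader might infer that no safety question exists anywhere. The documents show only that none is described. The survey items are not supplied, and neither is the manual of operations cited in Section 18.
- **Band irritation.** Its absence from the examples in Section 15 is not an omission, because the instruction covers any potential event.
- **Other routes.** The monitor's monthly review, and staff contact with non-adherent or withdrawing participants (Section 16), could bring to light events that affect participation. They are not symptom questions and would miss mild events.
- **Technique-specific attribution.** It is tempting to say that solicited data would show which technique causes symptoms. With up to 60 people, consecutive two-week blocks and no washout described, effects could carry into the next block and counts would be small. That benefit should not be claimed.
- **Proportionality.** The protocol template requires a specific monitoring plan only above minimal risk, and this plan already names a clinician monitor. This argues for a light remedy, not for none.
- **Assumed numbers.** The reporting fractions are assumptions, and a single recall question would not give complete capture either. The 4.9% is thus a best case.

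**Conclusion.** The point holds as a cheap improvement to safety capture. The only collection described is spontaneous, in a remote trial that expects mild events, already surveys participants every two weeks, and gives them reasons not to report. A low count could not be read as a low rate. If half of events were reported, zero reports in 60 would be compatible with a true proportion of up to about 9.7% instead of 4.9%. That figure rests on the assumed reporting fraction and on all 60 places being filled.

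The point does not contradict the daily-life-risk premise, and it does not affect the feasibility objective or the pooled efficacy analysis. It falls away, apart from a sentence to be added to the protocol, if the survey instruments already carry such an item.

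**What to change.** - **Add one fixed question** to each existing two-weekly survey, and once at the end of baseline through the existing text channel. It would ask about the past two weeks: muscle soreness, unusual fatigue, skin irritation from the band, a fall or injury, or any other health problem, with free text if yes. Placing it last would limit any influence on the satisfaction and self-efficacy answers.
- **Send positive answers** to the coordinator for follow-up and to the safety monitor.
- **Report solicited events descriptively**, baseline versus intervention, per two-week recall period and with the number who answered. Keep spontaneous reports separate, and make no attribution to individual techniques.
- **Reconcile the rules it touches.** Section 16 makes self-reported side effects a ground for withdrawal without consent, so solicited answers would feed that rule. The protocol must state how the two fit together. Section 15, Part I gives the monitor immediate notice of serious events, while Section 18 does so for any adverse event. These must also agree.
- **If such an item already exists**, describe it in Sections 11 and 15.

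The cost is one question at five contacts (four surveys and the end of baseline), some coordinator time, and a reported count that will look higher. Until Section 16 is reconciled, asking could also increase withdrawals.
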